9.5.4.2 Reporting of Pregnancy and Exposure to Study Drug Through Breastfeeding

Any pregnancy in which the estimated date of conception is either before the last visit or within 28 days of last study treatment, or any exposure to study drug through breastfeeding during study treatment or within 28 days of last study treatment, must be reported.

If an adverse outcome of a pregnancy is suspected to be related to study drug exposure, this should be reported regardless of the length of time that has passed since the exposure to study treatment.

A congenital anomaly, death during perinatal period, an induced abortion, or a spontaneous abortion are considered to be an SAE and should be reported in the same time frame and in the same format as all other SAEs (see Reporting of SAEs [[Section 9.5.4.1](#)]).

Pregnancies or exposure to study drug through breastfeeding must be reported by fax or email as soon as possible but no later than 1 business day from the date the investigator becomes aware of the pregnancy. The contact information for the reporting of pregnancies and exposure to study drug through breastfeeding is provided in the Investigator Study File. The Pregnancy Report Form must be used for reporting. All pregnancies must be followed to outcome. The outcome of the pregnancy must be reported as soon as possible but no later than 1 business day from the date the investigator becomes aware of the outcome.

A subject who becomes pregnant must be withdrawn from study treatment.

9.5.4.3 Reporting of Events Associated with Special Situations

9.5.4.3.1 REPORTING OF ADVERSE EVENTS ASSOCIATED WITH STUDY DRUG OVERDOSE, MISUSE, ABUSE, OR MEDICATION ERROR

AEs associated with study drug overdose, misuse, abuse, and medication error refer to AEs associated with uses of the study drug outside of that specified by the protocol. Overdose, misuse, abuse, and medication error are defined as follows:

Overdose	Accidental or intentional use of the study drug in an amount higher than the protocol-defined dose
Misuse	Intentional and inappropriate use of study drug not in accordance with the protocol
Abuse	Sporadic or persistent intentional excessive use of study drug accompanied by harmful physical or psychological effects
Medication error	Any unintentional event that causes or leads to inappropriate study drug use or subject harm while the study drug is in the control of site personnel or the subject.

All AEs associated with overdose, misuse, abuse, or medication error should be captured on the Adverse Event eCRF and also reported using the procedures detailed in Reporting of SAEs (Section 9.5.4.1) even if the AEs do not meet serious criteria. Abuse is always to be captured as an AE. If the AE associated with an overdose, misuse, abuse, or medication error does not meet serious criteria, it must still be reported using the SAE form and in an expedited manner but should be noted as nonserious on the SAE form and the Adverse Event eCRF.

9.5.4.3.2 REPORTING OF STUDY-SPECIFIC EVENTS

Study-specific events (as detailed in Section 9.5.1.5.2) should always be considered as serious important medical events and be entered on the Adverse Event eCRF and reported using the procedures detailed in Reporting of SAEs (Section 9.5.4.1), even if the study-specific event does not meet other serious criteria.

9.5.4.4 Expedited Reporting

The sponsor must inform investigators (or as regionally required, the head of the medical institution) and regulatory authorities of reportable events, in compliance with applicable regulatory requirements, on an expedited basis (ie, within specific time frames). For this reason, it is imperative that sites provide complete SAE information in the manner described above.

9.5.4.5 Breaking the Blind

In the case of a medical emergency where the appropriate treatment of the subject requires knowledge of the study treatment given, the investigator may break the randomization code for an individual subject. In all such cases, the AE necessitating the emergency blind break will be handled as an SAE in accordance with the procedures indicated above. Any broken code will be clearly justified and documented. The medical monitor must be notified immediately of the blind break.

9.5.4.6 Regulatory Reporting of AEs

AEs will be reported by the sponsor or a third party acting on behalf of the sponsor to regulatory authorities in compliance with local and regional law and established guidance. The format of these reports will be dictated by the local and regional requirements.

All studies that are conducted within any European country will comply with European Good Clinical Practice Directive 2005/28/EC and Clinical Trial Directive 2001/20/EC. All SUSARs will be reported, as required, to the competent authorities of all involved European member states.

9.5.5 Completion/Discontinuation of Subjects

A subject may elect to withdraw from the study at any time for any reason. All subjects who discontinue study drug early for any reason will undergo an ED Visit within 7 days of their

last dose of study drug (see [Section 9.1.2.2](#)). In addition, Follow-Up Visits will be scheduled 4 and 12 weeks after the last dose of study drug (Visit 14 and Visit 15, respectively) (see [Section 9.1.2.2](#)). These Follow-Up Visits will be conducted to monitor efficacy and safety parameters after early withdrawal from the study or discontinuation of study drug. See [Table 3](#) for full details of the assessments to be performed at these visits.

All subjects who discontinue study drug before reaching 12 months of treatment will also be asked to return to the clinic for a 12 month clinical assessment and then again at 24 months. Subjects who discontinued treatment between 12 and 24 months of treatment will be asked to return to the clinic for a 24 month clinical assessment. Subjects who discontinue early from study drug are considered “on study” as long as they continue to return for their clinical assessments at 12 and 24 months as outlined above, at which efficacy and quality of life will be assessed along with concomitant medications and AEs. However, subjects who discontinue study drug early are not considered to have ‘completed’ the study as a final Subject Disposition. A subject removed from the study for any reason may not be replaced.

The investigator will promptly explain to the subject involved that the study will be discontinued for that subject and provide appropriate medical treatment and other necessary measures for the subject. A subject who has ceased to return for visits will be followed up by mail, phone, or other means to gather information such as the reason for failure to return, the status of treatment compliance, the presence or absence of AEs, and clinical courses of signs and symptoms.

The primary reasons for early withdrawal from the study are: AE, lost to follow-up, subject choice, withdrawal of consent, pregnancy, study terminated by sponsor, and other. The secondary reasons for early withdrawal from the study are: AE, subject choice, and other.

The primary reasons for early discontinuation from the study drug are: AE, subject choice, pregnancy, inadequate therapeutic effect, and other. The secondary reasons for early discontinuation from the study drug are: AE, subject choice, inadequate therapeutic effect, and other.

9.5.6 Abuse or Diversion of Study Drug

AEs associated with abuse or diversion will be appropriately reported as AEs and monitored per [Section 9.5.1.5.1](#). Abuse is always to be captured as an AE.

During the study, the investigator should be aware of the possibility of abuse or diversion of study drugs and should report any concern about mishandling, abuse, loss, theft, or diversion of study drugs by completing the Abuse or Diversion of Study Drug eCRF.

9.5.7 Confirmation of Medical Care by Another Physician

The investigator will instruct subjects to inform site personnel when they are planning to receive medical care by another physician. At each visit, the investigator will ask the subject whether he or she has received medical care by another physician since the last visit or is

planning to do so in the future. When the subject is going to receive medical care by another physician, the investigator, with the consent of the subject, will inform the other physician that the subject is participating in the clinical study.

9.6 Data Quality Assurance

This study will be organized, performed, and reported in compliance with the protocol, standard operating procedures, working practice documents, and applicable regulations and guidelines. Site audits will be made periodically by the sponsor's or the CRO's qualified compliance auditing team, which is an independent function from the study team responsible for conduct of the study.

9.6.1 Data Collection

Data required by the protocol will be collected on the eCRFs and entered into a validated data management system that is compliant with all regulatory requirements. As defined by ICH guidelines, the CRF is a printed, optical, or electronic document designed to record all of the protocol-required information to be reported to the sponsor on each study subject.

Data collection on the eCRF must follow the instructions described in the CRF Completion Guidelines. The investigator has ultimate responsibility for the collection and reporting of all clinical data entered on the eCRF. The investigator or designee as identified on Form FDA 1572 (where applicable) must sign the completed eCRF to attest to its accuracy, authenticity, and completeness.

Completed, original eCRFs are the sole property of Eisai and should not be made available in any form to third parties without written permission from Eisai, except for authorized representatives of Eisai or appropriate regulatory authorities.

9.6.2 Clinical Data Management

All software applications used in the collection of data will be properly validated following standard computer system validation that is compliant with all regulatory requirements. All data, both eCRF and external data (eg, laboratory data), will be entered into a clinical system.

Electronic source (eSource) methodology may be used for some of the clinical efficacy and HRQoL assessments performed in this study.

9.7 Statistical Methods

All statistical analyses will be performed by the sponsor or designee. Statistical analyses will be performed using SAS software or other validated statistical software as required.

All statistical tests will be based on the 5% (2-sided) level of significance, unless specified.

9.7.1 Statistical and Analytical Plans

All statistical analyses will be performed by the Sponsor or designee after the study is completed and the database is locked and released for unblinding.

9.7.1.1 Study Endpoints

9.7.1.1.1 PRIMARY ENDPOINT

The primary endpoint of the study is:

- Change from baseline in the CDR-SB at 24 months.

9.7.1.1.2 SECONDARY ENDPOINTS

The secondary endpoints of the study are:

- Time to worsening of CDR scores by 24 months (eg, the worsening of global CDR score is defined as an increase from baseline by at least 0.5 points on the global CDR scale on 2 consecutive scheduled visits at which global CDR is undertaken)
- Time to conversion to dementia for subjects who were not clinically staged as dementia at Baseline based on clinical diagnosis
- The rate of change over time (mean slope) based on CDR-SB score over 24 months
- Change from baseline in CDR-SB at 27 months (ie, 24 months of treatment plus 3 months posttreatment follow-up)
- Change from baseline in ADAS-cog₁₄, MMSE, and FAQ at 24 months
- Change from baseline in ADAS-cog₁₄ Word List (immediate recall and delayed recall) at 24 months

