The CDR will be conducted every 3 months during the Core Study; other cognitive and functional assessment instruments will be administered every 6 months. Every 3 months, the investigator is required to confirm the clinical staging of AD (ie, dementia or nondementia). This staging decision will be verified via a central review process and adjudicated if necessary (adjudication will only occur when there is a discrepancy between the clinical disease staging made by the site compared to that determined by the central review process; moreover, where adjudication is required, it will be undertaken by an independent assessor(s)).

The health-related quality of life measures will be conducted every 6 months during the Core Study, along with the NPI-10.

MRI scans (including vMRI and fMRI) will be performed at 12 and 24 months during the Core Study or at the ED visit.

At every visit, AEs will be assessed, concomitant medications will be reviewed, physical examinations with dermatologic review by the study investigator will be performed, vital signs and respiratory rate will be measured, suicidality will be assessed, blood will be drawn for clinical chemistry, hematology, and for immunologic assessments. A urine sample will be provided for dipstick urinalysis. Other assessments, including safety assessments (neurologic exams, ECGs, urine pregnancy tests for females of child-bearing potential), and blood draws for PK, PD and assessment of immune status are performed at different intervals throughout the treatment period of the study.

For subjects who consent to the amyloid PET longitudinal substudy, amyloid PET will be conducted after 12 and 24 months of treatment during the Core Study (or at the ED visit, provided the subject has received at least 39 weeks of study drug). For subjects who consent to the CSF longitudinal substudy, CSF will be collected after 24 months of treatment during the Core Study (or at the ED visit, provided the subject has received at least 39 weeks of study drug). Note that subjects who are assessed by both amyloid PET and CSF A β (1-42) are required to wait for a minimum of 48 hours between the 2 procedures. (revised per Amendment 01) Please refer to Schedule of Assessments ([Table 3](#)).

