9.1.2.2 Follow-Up Period

All subjects, regardless of whether they complete all 24 months of treatment or discontinue study drug prematurely, will complete 2 post-treatment Follow-Up Visits; one 4 weeks after the last dose of study drug and a second 12 weeks after the last dose of study drug (Visit 14 and Visit 15 respectively). If clinically indicated, more frequent safety assessments can be made as unscheduled (UNS) assessments or visits during the post-treatment follow-up period.

In some cases, UNS visits will be needed to follow-up on safety or other findings, and the related assessments (outlined in the Schedule of Assessments) will depend on the reason for the UNS visit, and will be decided at the discretion of the investigator.

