^b Subjects who discontinue taking study drug prematurely for any reason will undergo an ED Visit within 7 days of their last dose of study drug. In addition, Follow-Up Visits will be scheduled 4 and 12 weeks after the last dose of study drug (Visit 14 and Visit 15, respectively). Subjects who discontinue study drug before reaching 12 months of treatment will also be asked to return to the clinic for a 12 month clinical assessment and then again at 24 months. Subjects who discontinue treatment between 12 and 24 months of treatment will be asked to return to the clinic for a 24 month clinical assessment. Subjects who discontinue early from study drug are considered “on study” as long as they continue to return for their clinical assessments at 12 and 24 months as outlined above, at which efficacy (MMSE, CDR, ADAS- cog₁₄) and quality of life (EQ-5D, QOL-AD and Zarit’s Burden Interview) will be assessed along with concomitant medications and AEs. These 12 and 24 month clinical assessment visits do not need to be attended if they fall within 8 days (visit window) after the ED Visit or within ±8 days of either of the Follow-Up Visits (Visit 14 and Visit 15).

^c All subjects, regardless of whether they complete all 24 months of treatment or discontinue study drug prematurely, will complete 2 posttreatment Follow-Up Visits; one 4 weeks after the last dose of study drug and a second 12 weeks after the last dose of study drug (Visit 14 and Visit 15 respectively). If clinically indicated, more frequent safety assessments can be made as UNS assessments or visits during the posttreatment Follow-Up Period. Subjects who have a Grade 2 or greater lymphocytopenia (less than 800/mm³) during the follow-up period (ie, at either Visit 14 or Visit 15) should have ALC measured every 4 weeks until resolution or confirmation of a non drug-related cause of the lymphocytopenia. ALC will be derived from the CBC with differential representing the normal lymphocytes (with atypical lymphocytes removed and presented as a separate count if they are present) and calculated by the white blood cell count × percentage of lymphocytes. (revised per Amendment 01)

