9.7.1.6.2 SECONDARY EFFICACY ANALYSES

The secondary analyses will be performed only if the primary analysis is significant. The treatment effect for elenbecestat (E2609) 50 mg/day versus placebo, for each secondary efficacy endpoint, will be tested using a sequential testing procedure at a significance level of 2-sided alpha = 0.05, ie, any test will start only if the test with higher hierarchical order is

significant. The final hierarchical order will be specified later in the statistical analysis plan before database lock.

Time to worsening of CDR scores by 24 months will be analyzed on the FAS using Cox regression model for treatment effect adjusting for randomization stratification factors. Time to worsening of a CDR score is defined as time from randomization to worsening of the CDR score (ie, the first worsening in 2 consecutive scheduled visits). For subjects whose CDR scores have not worsened by the end of study, the time to worsening of the CDR score will be censored at the date of last CDR assessment for these subjects.

Time to conversion to dementia for subjects who were not clinically staged as dementia at Baseline based on clinical diagnosis will be analyzed on the FAS using Cox regression model for treatment effect adjusting for randomization stratification factors. Proportion of subjects with dementia diagnosis at 24 months will be estimated using Kaplan—Meier method based on time to conversion to dementia based on clinical diagnosis. Time to conversion to dementia for subjects who were not clinically staged as dementia at Baseline based on clinical diagnosis is defined as time from randomization to conversion to dementia based on clinical diagnosis. For subjects without clinical dementia by the end of study, the time to conversion to dementia based on clinical diagnosis will be censored at the date of last dementia diagnosis.

The rate of change over time (mean slope) based on change from baseline in the CDR-SB will be analyzed using linear mixed effects (LME) models for multivariate normal data derived from a random coefficient model (slope analysis), where the mean slope in each group depends on a continuous assessment time. The LME model will include baseline CDR-SB, randomization stratification variables, assessment time, and treatment group-by-assessment time.

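### Time to CDR worsening: most subjects who stop drug cannot have a worsening first seen at month 24 confirmed, yet stay at risk to that date, so unequal discontinuation can bias the hazard ratio

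*Protocol*

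**What the plan says.** Protocol 9.7.1.1.2 gives, as its worked example of the event, a rise of at least 0.5 from baseline "on the global CDR scale on 2 consecutive scheduled visits at which global CDR is undertaken". Section 9.7.1.6.2 dates the event at the first of the two visits ("ie, the first worsening in 2 consecutive scheduled visits"). Its censoring rule for anyone still without an event when the study ends reads: "the time to worsening of the CDR score will be censored at the date of last CDR assessment for these subjects". The model is stated as "Time to worsening of CDR scores by 24 months will be analyzed on the FAS using Cox regression model", adjusted for the stratification factors. The endpoint is tested in a fixed sequence at two-sided 0.05, and only if the primary analysis is significant.

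The CDR calendar depends on drug status. On drug, "The CDR will be conducted every 3 months during the Core Study". Table 3 also marks a CDR at the early discontinuation (ED) visit and at Visits 14 and 15. Those two visits are tied to the last dose: "one 4 weeks after the last dose of study drug and a second 12 weeks after the last dose of study drug" (9.1.2.2). Under Table 3 note b, subjects who stop before month 12 "will also be asked to return to the clinic for a 12 month clinical assessment and then again at 24 months". For later stoppers, "Subjects who discontinue treatment between 12 and 24 months of treatment will be asked to return to the clinic for a 24 month clinical assessment". No further CDR is scheduled after that off-drug month-24 assessment.

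**The concern.** A rule that needs a second visit to create an event, combined with censoring at the last visit, gives event-free credit for a final interval in which no event could have been registered. For completers the final interval is harmless, because Visits 14 and 15 follow month 24. For most discontinuers it is not. Whether a worsening can count then depends on drug status, while time at risk is credited regardless.

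If one arm discontinues more, it registers fewer events for the same true course of disease. The protocol makes some imbalance plausible. Section 9.5.1.5.5 requires stopping for moderate to severe rash or any rash beyond 72 hours, and for moderate to severe oral or genital herpes. Section 9.3.3 requires it after a second confirmed lymphocytopenia within 6 months. Section 7.1 lists drug rash and orolabial herpes relapse among the events of interest in the multiple-dose study.

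The follow-up window is also unsettled. The endpoint is defined by 24 months, but event-free subjects are followed to the end of study, which for completers is month 27, after 3 months off drug.

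**Working it through.** **The plan's own figure.** The protocol gives no event count, hazard ratio or power for this endpoint, only a sample size for the primary (9.7.2). The difference is 0.25 × 1.75 = 0.4375, with SD 2.05, 90% power and two-sided 0.05. So n = 2 × (1.960 + 1.282)² × 2.05² / 0.4375² = 462 per arm, and 462 / 0.70 = 660 per arm against the stated 665. The figure reproduces, and 665 per arm is used below.

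**Calendars side by side (days from Table 3).**
- Completer, onset day 600: seen at Visit 12 (day 638), confirmed at Visit 13 (day 729), event at day 638. An onset first seen on day 729 can be confirmed on day 757 or 813.
- Stops on day 426: CDR at ED, day 426 + 28 = 454, day 426 + 84 = 510, then day 729. An onset on day 600 is first seen on day 729, has no later CDR, and is censored event-free on day 729. The blind interval is 729 − 510 = 219 days.
- Stops on day 100: CDR at ED, days 128 and 184, then 365 and 729. Any onset after day 365 is first seen on day 729. The blind interval is 364 days.
- Stops after day 729 − 84 = 645: Visit 15 falls after month 24, so confirmation is possible.

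**Inputs assumed, not in the protocol.** 24-month worsening 40% (30% to 50% gives similar results); discontinuation by arm 30/30, 35/25 or 40/20%; all, half or none of the discontinuers return; exponential and persistent onset; true hazard ratio 1; Cox model with treatment only.

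**Events lost.** At 30/30 with all returning, 11.5% of discontinuers have a month-24 worsening that cannot be confirmed, about 30% of the worsenings among returning discontinuers. In completers it is 0%. Per arm: 0.30 × 11.5% = 3.45%, and 665 × 0.0345 ≈ 23 subjects. About 10% of discontinuers stop late enough to have Visit 15 after month 24.

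**Crude check, all returning.** Compare the proportions of subjects counted as events:
- 35/25: 4.11% against 2.86% of each arm lost (665 × 0.0411 ≈ 27 and 665 × 0.0286 ≈ 19). Ratio (40 − 4.11) / (40 − 2.86) = 35.89 / 37.14 = 0.966.
- 40/20: 4.73% against 2.26% lost (665 × 0.0473 ≈ 31 and 665 × 0.0226 ≈ 15). Ratio (40 − 4.73) / (40 − 2.26) = 35.27 / 37.74 = 0.935.

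**Simulated null hazard ratio under the stated rule** (Monte Carlo error about 0.01 in the smaller runs):

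| Discontinuation | All return | Half return | None return |
|---|---|---|---|
| 30/30 | 1.00 | 0.99 to 1.00 | about 1.00 |
| 35/25 | 0.96 to 0.97 | 0.98 to 0.99 | 0.98 to 1.00 |
| 40/20 | 0.93 | 0.95 to 0.96 | 0.99 to 1.00 |

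If CDRs after month 24 may not confirm an event, completers lose onsets first seen at month 24 too. With all returning, the ratio is then 0.973 (35/25) and 0.949 (40/20).

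**False findings.** With 665 per arm and 40% worsening, the chance of a false finding favouring the arm with more discontinuation, nominally 2.5%, is 5.7% at 35/25 (3.5% if half return) and 10.6% at 40/20 with full return. At 30/30 it is 2.5%.

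**Alternative rule.** Censoring at the last CDR that has a later CDR gives 1.00 to 1.02 across the scenarios tried.

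**The case against.** The definition is introduced as an example, and the treatment of an unconfirmed last-visit worsening is often left to the SAP. That is fair for the event definition. It does not cover the censoring rule or the off-drug calendar, both of which this protocol fixes, and no SAP can create a CDR that was never scheduled.

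The size rests on figures the protocol does not give. Section 9.7.2 has one 30% dropout rate, not split by arm. Discontinuers are only asked to return, and dividing by 0.70 in effect treats the 30% as giving no month-24 value. If nobody returned, the bias would all but vanish. This objection stands and limits the claim.

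Several stronger readings are tempting and should be resisted:
- That no off-drug subject can confirm a month-24 worsening. Those stopping within about 12 weeks before month 24 can.
- That the endpoint favours active drug. The direction follows whichever arm stops more, and no rates by arm are given at 50 mg. The lymphocyte rule interrupts drug first and stops it permanently only on a second confirmed occurrence within 6 months.
- That the trial's error rate rises to 5% or 10%. Secondaries are tested only after a significant primary, so under a global null that gate caps false claims. The quoted rates need a real CDR-SB effect with none on global CDR, although both scores come from the same interview.

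**Conclusion.** The concern holds in a conditional form. As written, the confirmation rule, the censoring rule and the off-drug calendar together credit most returning discontinuers with event-free time in which no event could be registered. This is a consequence of stated rules, not a missing detail. The null hazard ratio moves by roughly 1 to 4% at a 10-point imbalance in discontinuation and 4 to 7% at a 20-point imbalance, when half to all discontinuers return. With equal discontinuation the cost is lost events only. Those scenarios are assumptions, and the simulations behind the table take worsening as persistent and rated without error. The conflict between a 24-month endpoint and follow-up to end of study needs settling whatever the discontinuation rates turn out to be. One gated secondary endpoint is affected. It should be corrected before unblinding.

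**What to change.** In 9.7.1.6.2 and the SAP, state for both arms alike:
- A subject without a confirmed event is censored at the last CDR on or before Visit 13 that is followed by another scheduled CDR able to confirm it.
- Visits 14 and 15 serve only to confirm a worsening first seen by month 24. They add no event dates and no follow-up time.
- As a sensitivity analysis, also count a worsening present at the subject's last scheduled CDR up to month 24.

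The last version is better kept as sensitivity. It removes the bias when ratings are error-free (0.99 to 1.01). With 5% misrating per visit, 40/20 discontinuation and no return, it drifts to about 1.03, against the arm with more discontinuation, and it gives up the purpose of confirmation.

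The cost is wording, a few events and some follow-up time. An alternative is to add a confirmatory CDR after the off-drug month-24 visit. It gives 0.99 to 1.00 and keeps the events, but adds a visit.
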